## 5.2 Subject Exclusion Criteria

**Subject Exclusion Criteria:** Subjects eligible for this study must not meet any of the following criteria:

1. Life expectancy  $< 4$  months;
2. Subjects with radiographic evidence of central nervous system (CNS) metastases as assessed by computerized tomography (CT) or magnetic resonance imaging (MRI) that are not well controlled (symptomatic or requiring control with continuous corticosteroid therapy [e.g., dexamethasone]). Note: Subjects with CNS metastases are permitted to participate in the study if the CNS metastases are medically well controlled prior to screening (as assessed by the Investigator) after receiving local therapy (irradiation, surgery, etc.);

Protocol: A Phase 2 Open Label, Multi-Center, Multinational Study Investigating The Efficacy and Safety Of GTx-024 On Advanced, Androgen Receptor-Positive Triple Negative Breast Cancer (AR+ TNBC)	Compound No.: GTx-024 Author: [name]
---	---

3. Radiotherapy within 14 days prior to the first dose of study treatment;
4. Have, in the judgment of the Investigator, a clinically significant concurrent illness or psychological, familial, sociological, geographical, or other concomitant condition that would not permit adequate follow-up and compliance with the study protocol;
5. Positive hepatitis B virus (HBV) and/or hepatitis C virus (HCV) infection at screening;
6. Positive human immunodeficiency virus (HIV) infection at screening;
7. Prior treatment with any anti-androgens, including but not limited to, enzalutamide and bicalutamide;
8. Major surgery within 28 days of the first dose of study treatment;
9. Be currently taking or have previously taken testosterone, methyltestosterone, oxandrolone (Oxandrin®), oxymetholone, danazol, fluoxymesterone (Halotestin®), testosterone-like agents (such as dehydroepiandrosterone, androstenedione, and other androgenic compounds, including herbals), or anti-androgens;
10. Treatment with any of the following hormone replacement therapies, unless discontinued at least 28 days prior to the first dose of study treatment:
  - Estrogens
  - Megesterol acetate;
11. Treatment with any investigational agent within 28 days before the first dose of study treatment;

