## 6.6 Concomitant Medications/Treatments

Forbidden medications and treatments during the study duration include:

- Major surgery within 28 days before the first dose of study treatment;
- Testosterone, methyltestosterone, oxandrolone (Oxandrin®), oxymetholone, danazol, fluoxymesterone (Halotestin®), testosterone-like agents (such as dehydroepiandrosterone, androstenedione, and other androgenic compounds, including herbals), Previous therapy with testosterone and testosterone-like agents is acceptable with a 28-day washout (if previous testosterone therapy was long-term depot within the past 6 months, the site should contact the Medical Monitor)
- Any prior or current use of anti-androgens including enzalutamide and bicalutamide;
- Treatment with any of the following hormone replacement therapies within 28 days before the first dose of study treatment:
  - Estrogens
  - Megesterol acetate;
- Treatment with any investigational agent within 28 days before the first dose of study treatment;
- Local palliative radiotherapy or localized radiotherapy for lytic lesions at risk of fracture within 7 days prior to the first dose of study treatment;
- Radiotherapy within 14 days prior to the first dose of study treatment.. Subjects must have recovered from radiotherapy toxicities prior to the first dose of study treatment;
- Any antineoplastic treatment (including, but not limited to chemotherapy);.

Protocol: A Phase 2 Open Label, Multi-Center, Multinational Study Investigating The Efficacy and Safety Of GTx-024 On Advanced, Androgen Receptor-Positive Triple Negative Breast Cancer (AR+ TNBC)	Compound No.: GTx-024 Author: [name]
---	---

- Caution should be exercised when administering potent CYP3A4 inducers, UDP inhibitors, and substrates of BCRP with GTx-024. Drug-drug interaction studies conducted with GTx-024 3 mg have demonstrated that concomitant use of CYP3A4 inducers may decrease the rate and extent of exposure of GTx-024 and its glucuronide metabolite. UDP inhibitors may increase GTx-024 and glucuronide exposure. Concomitant administration of GTx-024 with BCRP substrates may lead to increased exposure of the BCRP substrate.

Protocol: A Phase 2 Open Label, Multi-Center, Multinational Study Investigating The Efficacy and Safety Of GTx-024 On Advanced, Androgen Receptor-Positive Triple Negative Breast Cancer (AR+ TNBC)	Compound No.: GTx-024 Author: [name]
---	---

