### 7.1 Screening

For potential subjects without documented evidence of AR+ status, a Prescreening period is allowed any time prior to the Screening assessment (Visit 1), in order to determine AR status through a local laboratory. Should your institution require consent from the potential subject for prescreening tests, a separate prescreening consent should be obtained. Subjects will not be assigned a study number during the Prescreening period. Once AR status is determined to be positive, the potential subject must sign the full study consent form and may proceed to the Screening Visit (Visit 1).

Screening assessments must occur within 28 days prior to the first dose of study treatment for determination of subject's overall eligibility. Informed consent will be obtained from the subjects before performing any other study procedure or test. AEs will be collected from the signing of the informed consent form (ICF). The following tests and procedures will be performed during the screening visit (Visit 1):

- Eligibility criteria check
- Subject medical history (current and past)
- Demography (age, gender, race)
- Diagnosis and extent of cancer
- Review of prior/concomitant medications, including previous and current anticancer treatment
- Physical examination, including height, weight, and vital signs (heart rate, respiratory rate, temperature, blood pressure in a sitting position)
- ECOG performance status
- ECG
- Blood sampling for: screening for HIV, HBV, and HCV

Protocol: A Phase 2 Open Label, Multi-Center, Multinational Study Investigating The Efficacy and Safety Of GTx-024 On Advanced, Androgen Receptor-Positive Triple Negative Breast Cancer (AR+ TNBC)
	
Compound No.: GTx-024 Author: [name]

--	---

- Blood sampling for hematology, biochemistry, coagulation status, and serum pregnancy test (if applicable)
- Blood sampling for specific blood tests: PSA
- Urine analysis
- AE collection (from the moment of ICF signing)
- Radiological evaluation of the breast cancer (as applicable CT/MRI/bone scan). Imaging results will be confirmed by a central imaging facility, although a subject will be enrolled based on the local imaging and Investigator's assessment. The central imaging facility will also perform tumor volumetric assessment for the subjects undergoing CT scanning. It is recommended these procedures are done as close to the baseline visit as possible (if possible within 7 days prior to baseline)

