#### 11.4.2 Definition of analysis endpoints; primary, secondary, tertiary, exploratory, and safety

##### Primary efficacy endpoint

Tumor response in terms of clinical benefit will be assessed by RECIST 1.1 criteria from centrally read CT scans obtained at the 16 week assessment. Tumor response is judged relative to baseline tumor assessments. An evaluable subject will be considered to have a response of CB if the assessment indicates SD, PR, or CR. The primary assessment is among the evaluable subjects in the FAS at 16 weeks. An evaluable subject who does not have a week 16 assessment for any reason remains in the evaluable subset of the FAS and is considered a failure to achieve CB (SD, PR, or CR).

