Week/Day				Week 4	Week 8	Week 12	Week 16	Week 20	Week 24	Week 28	Every 8 weeks (± 7 days)	3 days after the last dose of GTx-024	
Procedure				Day 28 (± 7 days)	Day 56 (± 7 days)	Day 84 (± 7 days)	Day 112 (± 7 days)	Day 140 (± 7 days)	Day 168 (± 7 days)	Day 196 (± 7 days)			
GTx-024 18 mg dispensing/administration		X 			X		X		X		X		
GTx-024 18 mg accountability				X	X	X	X		X		X	X	
QoL EQ-5D-5L		X		X	X	X	X		X		X	X	
28 (± 2 days) Follow-up after last dose													X
Vital Status Follow-up (every 60 days after last dose) 													

Protocol: A Phase 2 Open Label, Multi-Center, Multinational Study Investigating The Efficacy and Safety Of GTx-024 On Advanced, Androgen Receptor-Positive Triple Negative Breast Cancer (AR+ TNBC)

Compound No.: GTx-024  
Author: [name]

-  Subjects with clinical benefit at 16 weeks will continue on therapy for up to 12 months (as long as they still benefit from the treatment during these 12 months). If so, the subjects will be asked to come for a visit every other month and undergo the assessments for the treatment period.
-  Visit 10 should occur at Week 32; i.e., 8 weeks after Visit 8 (Week 24).
-  AR status to be checked via nuclear AR staining by IHC, only if not available in the medical record of the subject. This assessment will be done in a local/regional laboratory. AR status assessed locally (or as per medical record) will be used to determine subject eligibility during a Prescreening or the study screening period. AR status will be confirmed by a central laboratory prior to Visit 2 (Day 1).
-  These medical procedures and assessments do not have to be repeated if done at screening within 7 days before the first dose of study treatment.
-  Vital Status Follow-up (every 60 days after last dose) for up to 24 months
-  HBV screening will be done as HBsAg.
-  Imaging study (CT, MRI) is recommended to be performed within 7 days prior to the first dose of study treatment. The imaging studies will be assessed by both a local imaging facility and a central reader. Subject eligibility will be based on local reading of the imaging studies. Medical decisions will be based on the local assessments.
- At visits V1, V6, V8, and EOT, tumor volumetric assessments will be done for the subjects undergoing CT scanning.

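### The baseline scan may predate radiotherapy or chemotherapy given before the first dose, so that treatment's effect can count as clinical benefit at week 16

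*Combined protocol and SAP*

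**What the plan says.** **Scan timing.** Section 7.1 sets the binding limit: "Screening assessments must occur within 28 days prior to the first dose of study treatment". Appendix A places CT/MRI and bone scan at Visit 1, Day -28 to -1. Footnote 7 of the schedule adds "Imaging study (CT, MRI) is recommended to be performed within 7 days prior to the first dose of study treatment", and Section 7.1 asks for imaging close to baseline, "if possible within 7 days prior to baseline". Neither shorter timing is mandatory.

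**Radiotherapy.** Exclusion 3 in Section 5.2 reads "Radiotherapy within 14 days prior to the first dose of study treatment". Section 6.6 repeats the 14-day limit but also lists "Local palliative radiotherapy or localized radiotherapy for lytic lesions at risk of fracture within 7 days prior to the first dose of study treatment".

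**Other anticancer treatment.** Inclusion 3 requires one or two prior chemotherapy regimens. Inclusion 14 asks only that their toxicity has resolved or is Grade 1. Section 6.6 forbids antineoplastic treatment during the study but gives no interval before the first dose. Major surgery and investigational agents each carry a 28-day limit, which matches the scan window.

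**Endpoint.** Section 11.4.2 states: "Tumor response is judged relative to baseline tumor assessments". SD, PR or CR at week 16 on central reading is a success. For non-measurable disease only, Section 3.2.1 defines SD as non-CR/non-PD. Inclusion 7 admits bone-only non-measurable disease.

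**The concern.** Response is a comparison of two scans. If an effective treatment falls between the first scan and the first dose of GTx-024, the comparison measures both treatments together. The trial has no control arm to separate them, and central reading does not help because the central reader uses the same early scan.

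The endpoint is sensitive to this. A subject succeeds if her disease has not progressed at week 16, and the decision rules need few successes: 2 of 21 to continue and 5 of 41 to declare efficacy. The risk is greatest where the treated site is most or all of the assessed disease, as with bone-only disease or one or two lesions. Section 6.6 itself names palliative and lytic-lesion radiotherapy, so treatment of this kind shortly before the first dose was foreseen.

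**Working it through.** **1. Exposed window.** Take a scan on Day -28, the earliest allowed.
- 14-day limit: Days -14 to -1 are barred, so radiotherapy is possible on Days -27 to -15. 27 - 15 + 1 = 13 days.
- 7-day palliative limit, if it governs: Days -27 to -8. 27 - 8 + 1 = 20 days.
- Chemotherapy: no interval is stated, so no bound can be calculated.

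Sections 7.1 to 7.3, 8.1 and 11.4.2 contain no rule that orders the scan after treatment or calls for a repeat.

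**2. The plan's own design.** Inputs from Sections 11.1 and 11.2: null rate 0.05, alternative 0.20, one-sided alpha 0.05, power 90%, continue at 2/21 or more, success at 5/41 or more. The exact probability of success at rate p is

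S(p) = Σ over x ≥ 2 of P[Bin(21, p) = x] × P[Bin(20, p) ≥ 5 - x].

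At p = 0.05:
- x = 2: 0.1981 × 0.0755 = 0.0150
- x = 3: 0.0660 × 0.2642 = 0.0174
- x = 4: 0.0156 × 0.6415 = 0.0100
- x ≥ 5: 0.0032

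The sum is 0.0457 before rounding of terms. S(0.20) = 0.902. A search for the smallest expected sample size under these constraints returns the same design, so the plan's figures reproduce.

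**3. Effect of misattributed CB.** The documents do not say how many subjects would be treated between scan and first dose, or how many of those would be scored CB for that reason alone. Both are assumed here. Their product d is added to the true rate of 0.05.

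| Treated after scan | Scored CB because of it | d | Apparent CBR | S |
|---|---|---|---|---|
| none | – | 0 | 0.0500 | 0.046 |
| 1% | 25% | 0.0025 | 0.0525 | 0.054 |
| 2% | 25% | 0.0050 | 0.0550 | 0.064 |
| 5% | 50% | 0.0250 | 0.0750 | 0.169 |
| 10% | 50% | 0.0500 | 0.1000 | 0.353 |

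If the increment applies only to subjects who would not otherwise benefit (0.05 + 0.95d), the last two values become 0.161 and 0.333. The range is essentially the same.

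**4. One misattributed CB for certain, all other subjects at 5%.**
- In stage 1: the other 20 subjects must supply at least one CB to pass, and at least four more CBs are needed overall. 0.3774 × 0.0755 + 0.1887 × 0.2642 + 0.0596 × 0.6415 + 0.0159 = 0.132. The chance of passing stage 1 rises from 0.283 to 1 - 0.95^20 = 0.642.
- In stage 2: 0.1981 × 0.2453 + 0.0660 × 0.6226 + 0.0189 = 0.109.

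**The case against.** The best counter-argument is that several things must coincide: a scan done early despite the recommendation, treatment in the gap, a treated site that decides the reading, and no progression or new lesion elsewhere for 16 weeks. Section 2.1 describes TNBC as often visceral and rapidly progressive. This stands. It is why the frequency is probably low and why the lower rows of assumed misattribution are at least as plausible as the upper ones.

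Section 6.6 might be said to close the gap, since screening is part of participation and antineoplastic treatment is forbidden during the study. The reading is possible but weak: the same list gives radiotherapy its own pre-dose limits, and a site would naturally follow those. The review of prior anticancer treatment at screening and at Day 1 would let affected subjects be identified, but no rule acts on it.

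Four stronger inferences are not supported:
- A reader might infer that radiotherapy alone is out of step with the scan window. It is not; chemotherapy has no stated interval at all.
- A reader might infer that the true error rate is 17% or 35%. Those values rest on assumed frequencies with no source in the documents.
- A reader might infer that scanning after radiotherapy removes the problem and restores 0.0457. It does not. A lesion irradiated on Day -20 and scanned on Day -7 could still be held stable to week 16 by the radiotherapy.
- A reader might infer that irradiated lesions will be followed as target lesions. The protocol defers to RECIST 1.1, whose rules it does not reproduce, so its silence settles nothing.

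**Conclusion.** The gap is real and lies in the text. Followed exactly, the plan allows a reference scan that predates radiotherapy or chemotherapy, and the effect of that treatment can contribute to CB. For radiotherapy the window is 13 days, or 20 under the 7-day limit. The 7-day and 14-day limits in Sections 5.2 and 6.6 contradict each other for palliative radiotherapy and must be reconciled; which should apply is not judged here.

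The size is uncertain. With assumed misattribution of 0.25 to 5 points, false success at a true CBR of 5% lies between about 0.054 and 0.35, against 0.046 by design. One misattributed CB for certain gives 0.109 to 0.132, more than double the design value. This is a narrow weakness, concentrated in subjects with bone-only disease or few lesions, and worth closing because the remedy is cheap and a single-arm trial cannot separate the two effects afterwards.

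**What to change.** 1. Amend footnote 7, in both copies of the schedule, and Section 7.1: the baseline scan used for response must be obtained after the last pre-study radiotherapy or other anticancer treatment and before the first dose; otherwise it is repeated.
2. Pre-specify in the SAP a sensitivity analysis of week-16 CBR that counts as non-CB any subject who received radiotherapy or other anticancer treatment between the baseline scan and the first dose, or whose CB rests only on a recently irradiated site. The SAP should define that last term in advance. This part addresses the stable disease that scan order cannot remove.
3. Reconcile the 7-day and 14-day radiotherapy limits in Sections 5.2 and 6.6.

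Items 1 and 2 leave N, the cut-offs and the eligibility criteria unchanged. An outright ban on following an irradiated site as the only disease is not proposed, because it could leave bone-only subjects admitted under inclusion 7 with nothing to assess. The cost is a short amendment, the recording of treatment dates and sites, and an occasional repeat scan. Sites that already scan within 7 days of the first dose will rarely need one.

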### 7.3 Treatment Phase

The first dose of study drug will be administered at baseline (Visit 2). GTx-024 will be administered for up to 12 months from the first dose of treatment or until disease progression (whichever is sooner), subject's withdrawal of consent, or intolerability. Subjects who benefit from the treatment at week 16 and still benefit from the treatment at week 24 may continue to receive GTx-024 for a total of 12 months from the date of the first dose of study treatment (as long as they still benefit from the treatment during these 12 months). Subjects who continue to demonstrate a beneficial response at 12 months will be offered to continue in a safety extension study under a separate protocol.

After randomization on Day 1, a safety check involving a comprehensive metabolic panel (Chem 14), including serum calcium and liver function tests, will be performed at Week 2 ( $\pm 3$  days). The Week 2 safety check should include a clinic visit. The investigator may repeat these checks at Week 3 ( $\pm 3$  days) if clinically indicated.

During the first 4 months of the treatment phase, the subjects will be asked to come for a visit every 4 weeks (Visits 3, 4, 5, and 6), and then every 8 weeks (Visit 8 and Visits 10–12 as required if still on treatment). Visits 7 and 9 at weeks 20 and 28 will only take place in subjects who have CR or PR at Visit 6 (week 16) or Visit 8 (week 24), respectively (see below).

The following tests and procedures will be performed during Visits 3, 4, 5, 6, and 8 in the treatment phase:

- Review concomitant medications
- Physical examination, including weight and vital signs (heart rate, respiratory rate, body temperature, blood pressure in a sitting position)
- ECOG performance status
- Blood sampling for: hematology, biochemistry, serum lipid profile, coagulation status, serum hormones, and PSA
- Urine analysis, only if clinically indicated
- Urine pregnancy test for premenopausal subjects (at the site)
- AE collection
- Subjects will be asked to complete a QoL questionnaire
- GTx-024 drug accountability/dispensation

Radiologic assessments for anti-tumor effect will be done every 8 weeks whilst subjects receive treatment (Visit 4, Visit 6, Visit 8, and thereafter). In addition, if a subject has CR or PR at Visit 6 (week 16) or Visit 8 (Week 24), in compliance with RECIST 1.1 guidelines, a confirmation of the CR or PR should be done 4 weeks later (i.e., Visit 7 and/or Visit 9, as

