## 7.7 Safety Checks and Unscheduled Visits

A page will be included in the eCRF that asks whether any unscheduled visits have taken place and provides space for the recording of any collected data, including unscheduled vital signs, ECG, and laboratory results. Early/late planned visits will not be considered to be unscheduled visits.

The laboratory results from the safety checks in Weeks 2 and 3 will be recorded on the unscheduled visit eCRF page.

Protocol: A Phase 2 Open Label, Multi-Center, Multinational Study Investigating The Efficacy and Safety Of GTx-024 On Advanced, Androgen Receptor-Positive Triple Negative Breast Cancer (AR+ TNBC)	Compound No.: GTx-024 Author: [name]
---	---

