	Day -28 to -1	Day 1		As required if still on treatment									
Visit number	V1	V2	Safety review Week 2 (±3 days)	V3	V4	V5	V6	V7	V8	V9	V10-V12 	VEOT  3 days after the last dose of GTx-024	VFU
Week/Day				Week 4	Week 8	Week 12	Week 16	Week 20	Week 24	Week 28	Every 8 weeks (± 7 days)		
Procedure				Day 28 (± 7 days)	Day 56 (± 7 days)	Day 84 (± 7 days)	Day 112 (± 7 days)	Day 140 (± 7 days)	Day 168 (± 7 days)	Day 196 (± 7 days)			
Serum lipid profile		X		X	X	X	X		X		X	X	
Coagulation status	X			X	X	X	X		X		X	X	
Serum hormones		X		X	X	X	X		X		X	X	
PSA	X	X 		X	X	X	X		X		X	X	X
CTC enumeration		X			X		X		X			X	
CTC gene expression		X										X	
Urine analysis	X	As clinically indicated											
Radiological evaluation: CT/MRI 	X				X		X	X 	X	X 	X	X	

Protocol: A Phase 2 Open Label, Multi-Center, Multinational Study Investigating The Efficacy and Safety Of GTx-024 On Advanced, Androgen Receptor-Positive Triple Negative Breast Cancer (AR+ TNBC)

Compound No.: GTx-024  
Author: [name]

Periods	Screening Day -28 to -1	Baseline Day 1	Safety check	Treatment phase  (from Baseline to EOT)								EOT/ Early termination	FU post treatment
Visit number	V1	V2	Safety review Week 2 (±3 days)	V3	V4	V5	V6	V7	V8	V9	V10-V12 	VEOT	VFU
Week/Day				Week 4	Week 8	Week 12	Week 16	Week 20	Week 24	Week 28	Every 8 weeks (± 7 days)	3 days after the last dose of GTx-024	
Procedure				Day 28 (± 7 days)	Day 56 (± 7 days)	Day 84 (± 7 days)	Day 112 (± 7 days)	Day 140 (± 7 days)	Day 168 (± 7 days)	Day 196 (± 7 days)			
Radiological evaluation: bone scan 	X				X		X	X 	X	X 			
Pharmacokinetic samples 		X		X		X	X		X				
ECG	X												
AEs	X	X		X	X	X	X		X		X	X	To be followed up to 28 days post treatment
Serum pregnancy test	X												
Urine pregnancy test 		X		X	X	X	X		X		X	X	X

Protocol: A Phase 2 Open Label, Multi-Center, Multinational Study Investigating The Efficacy and Safety Of GTx-024 On Advanced, Androgen Receptor-Positive Triple Negative Breast Cancer (AR+ TNBC)

Compound No.: GTx-024  
Author: [name]

Periods	Screening Day -28 to -1	Baseline Day 1	Safety check	Treatment phase  (from Baseline to EOT)								EOT/ Early termination	FU post treatment
Visit number	V1	V2	Safety review Week 2 (±3 days)	V3	V4	V5	V6	V7	V8	V9	V10-V12 	VEOT	VFU

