-  In compliance with RECIST 1.1 guidelines, subjects who have CR or PR at week 16 and/or week 24 require confirmation within a month as follows:
- For subjects with measurable lesions, subjects will undergo CT/MRI based on the Investigator's medical judgment
-  Bone scans will be performed at screening and then at weeks 8, 16, and 24 in only those subjects with baseline bone metastases, or if clinically indicated.
-  In compliance with RECIST 1.1 guidelines, subjects who have CR or PR at week 16 and/or week 24 require confirmation within a month as follows:
- For subjects with non-measurable lesions, subjects will undergo X-ray or bone-scanning based on the Investigator's medical judgment and location of disease.
-  Blood sampling for pharmacokinetic assessment. The exact time (hh:mm) and date of the blood sample should be recorded on the eCRF. At the baseline visit, the blood sample should be collected before the subject is given their first dose of GTx-024. At visits 3 (week 4), 5 (week 12), 6 (week 16), and 8 (week 24), the date and approximate time of the last dose of GTx-024 prior to the blood sample should also be recorded; i.e., it should be documented whether the subject took the previous dose that morning or the evening before.
-  Urine pregnancy tests will be done at the site with a pregnancy stick test in premenopausal patients. Postmenopausal patients are exempt from monthly urine pregnancy test.
-  First dose to be given at site during this visit.
-  A comprehensive metabolic panel (Chem 14), including serum calcium and liver function tests, will be performed at Week 2 ( $\pm 3$  days).

Abbreviations: AR = Androgen Receptor, BC = Breast Cancer, CR = complete response, CT = Computerized Tomography, CTCs, circulating tumor cells, ECG = Electrocardiogram, ECOG = Eastern Cooperative Oncology Group, eCRF = electronic case report form, EOT = End of Treatment, ER = Estrogen Receptor, FU = Follow-up, HBsAg = Hepatitis B surface Antigen, HBV = hepatitis B virus, HCV = hepatitis C virus, HER2 = Human Epidermal Growth Factor Receptor 2, HIV = Human Immunodeficiency Virus, ICF = Informed Consent Form, IHC = Immunohistochemistry, MRI = Magnetic Resonance Imaging, PR = partial response, QoL = Quality of Life, PSA = Prostate Specific Antigen, V = Visit.

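### Footnote 12 calls the urine pregnancy test monthly, but after week 16 the schedule gives it only every 8 weeks, leaving no test at weeks 20, 28, 36 and 44

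*Combined protocol and SAP*

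**What the plan says.** Three parts of the protocol bear on how often premenopausal subjects are tested while on drug.

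- **Footnote 12**, worded identically in the synopsis schedule and in Appendix A, says the test is a stick test done at the site in premenopausal patients, and then: "Postmenopausal patients are exempt from monthly urine pregnancy test".
- **The grid row** for the urine test, in both copies, is marked at Day 1, Visits 3 to 6 (weeks 4, 8, 12 and 16), Visit 8 (week 24), Visits 10 to 12, end of treatment (EOT) and follow-up. It is blank at Visit 7 (week 20) and Visit 9 (week 28). Footnote 1 says that, for those continuing, "the subjects will be asked to come for a visit every other month and undergo the assessments for the treatment period". Footnote 2 fixes the later visits: "Visit 10 should occur at Week 32; i.e., 8 weeks after Visit 8 (Week 24").
- **Section 7.3** sets the visit rhythm: "the subjects will be asked to come for a visit every 4 weeks (Visits 3, 4, 5, and 6), and then every 8 weeks". It adds that "Visits 7 and 9 at weeks 20 and 28 will only take place in subjects who have CR or PR at Visit 6" or Visit 8 respectively. Its pregnancy-test item, "Urine pregnancy test for premenopausal subjects (at the site"), stands in a list that covers Visits 3, 4, 5, 6 and 8 only.

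The protocol describes no home test or other interim test.

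**The concern.** An exemption from a monthly test makes sense only if those not exempt have one. After week 16 the grid does not provide it. Responders who attend at week 20 or 28 for confirmatory imaging are not tested there either, because the row is blank at both visits.

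Section 2.3.1 says the drug may affect a fetus, and Section 9.2.4 requires it to be stopped in pregnancy and the pregnancy reported within 24 hours. Those duties begin only once the pregnancy is recognised. The longer interval starts just when subjects with benefit settle into treatment of up to 12 months. Each carton holds 10 weeks of drug (Section 6.1.2), so dosing continues between tests. The trial enrols women from age 18, in a disease that Section 2.1 describes as more frequent below age 50.

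There is also a practical problem. A site that takes footnote 12 at its word would test every 4 weeks and a site that follows the grid would test every 8, so a monitor could not say with confidence what counts as a deviation.

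**Working it through.** The plan gives no figure to reproduce, so the check compares the schedule with a 4-weekly calendar.

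**Inputs**
- Marks in the urine-test row: both grids.
- Visit 10 at week 32 (footnote 2) and 8-weekly visits thereafter (Section 7.3), so Visit 11 = 32 + 8 = week 40 and Visit 12 = 40 + 8 = week 48.
- Visit window of ±7 days: Section 7 and the grid header.
- Treatment for up to 12 months: Section 7.3. I take this as 52 weeks, with EOT at week 52.

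**Post-baseline tests on treatment**

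| Schedule | Weeks | Tests |
|---|---|---|
| Grid | 4, 8, 12, 16, 24, 32, 40, 48, EOT | 8 + 1 = 9 |
| Every 4 weeks | 4, 8, 12, ..., 48, EOT | 12 + 1 = 13 |

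The difference is 13 − 9 = 4, and the absent weeks are 20, 28, 36 and 44. A subject treated past week 20, 28, 36 or 44 misses 1, 2, 3 or 4 tests respectively, so four is the maximum.

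**Gap between consecutive tests after week 16**
- Nominal: day 168 − day 112 = 56 days, against 28. Ratio 56 / 28 = 2.0.
- Earliest allowed to latest allowed: (168 + 7) − (112 − 7) = 70 days, against 28 + 14 = 42. Ratio 70 / 42 = 1.67.

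**Mean wait to the next scheduled test**

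Assume that a pregnancy becomes detectable at a uniformly random time between two tests. The mean wait is then half the gap: 56 / 2 = 28 days, against 28 / 2 = 14 days. This counts scheduled tests only.

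**How many subjects**

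The documents do not give the number of premenopausal subjects treated past week 16. A rough ceiling comes from assuming that the subjects who continue are those with clinical benefit at week 16, at the design rates of 5% to 20%:
- 41 evaluable subjects: 0.05 × 41 = 2.05 to 0.20 × 41 = 8.2, or about 2 to 8.
- All 55 enrolled, at the same rates: 0.05 × 55 = 2.75 to 0.20 × 55 = 11, or about 3 to 11.

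Only the premenopausal fraction of these is affected, and that fraction is unknown. Treatment decisions rest on the investigator's reading (Section 8.1), while the design rates refer to centrally read benefit, so the number continuing could differ.

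**The case against.** The strongest reply is that the case rests on one descriptive word. It occurs only where postmenopausal patients are exempted, while the grid header, footnote 1 and the visit rhythm in Section 7.3 all point to 8-weekly contact. Section 8 sends the reader to Appendix A for timing, so a site following the grid has one workable schedule. Deleting the word would remove the contradiction.

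Much of this stands. A reader might infer that the protocol orders monthly testing and that its own grid breaches the order. The documents do not support that, because no sentence states a monthly requirement. A reader might also infer that Section 7.3 itself schedules the test every 8 weeks to week 48. It does not: it gives that rhythm for visits, and its test item stops at Visit 8. The tests at weeks 32, 40 and 48 rest on the grid and footnotes 1 and 2.

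The existing safeguards are also substantial: a negative serum test at entry, non-hormonal contraception for sexually active women of childbearing potential during treatment and for 6 months after it, counselling, tests at EOT and follow-up, and the rules for stopping drug and reporting. A subject may recognise a pregnancy before any test, and one who stops drug between visits is tested at EOT.

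What does not stand is that the blanks might be damage from text extraction. Both copies of the row show them, and the Section 7.3 list independently omits Visits 7 and 9. Nor does deleting the word settle the safety question, since the interval would still double just as treatment becomes long, with no reason given.

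**Conclusion.** The point holds as a minor inconsistency in the safety schedule. Footnote 12 presupposes a monthly test and the grid does not deliver one after week 16. For a premenopausal subject still on drug, the interval between scheduled tests doubles nominally, and up to four tests are absent over a full year.

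The count of four assumes treatment past week 44 and a 4-weekly reading of monthly; subjects who stop earlier miss fewer. The mean-wait comparison depends on uniform timing. The number of subjects affected cannot be stated from the documents and is probably small.

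Nothing here touches the primary endpoint, the two-stage decision rules or any efficacy estimate. Nor do the documents show that pregnancies would go undetected: the effect is a longer wait for the next scheduled test.

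**What to change.** - **Grid, both schedules:** mark the urine test at Visits 7 and 9, to be done when those visits are held.
- **Weeks without a visit:** for premenopausal subjects still on treatment at weeks 20, 28, 36 or 44, use a home urine stick with the result reported by phone.
- **Footnote 12, both schedules:** reword to *every 4 weeks through EOT, at the site or at home in weeks without a visit*. The EOT and follow-up tests stay at the site.
- **Section 7.3:** move the pregnancy-test item out of the list for Visits 3, 4, 5, 6 and 8 into its own sentence covering all on-treatment weeks, including Visits 7 and 9 to 12, and allow the home test there. Changing only the place of testing would leave the list heading in conflict with the new footnote.
- **Positive result:** handle under Section 9.2.4.

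**Cost.** For a premenopausal subject treated past week 44: at most 4 sticks and 2 to 4 phone contacts (weeks 36 and 44 always, weeks 20 and 28 only if Visits 7 and 9 are not held). Fewer are needed for those who stop earlier. Section 7.7 offers a precedent for recording results: "The laboratory results from the safety checks in Weeks 2 and 3 will be recorded on the unscheduled visit eCRF page". The form layout is not in the documents, so a small eCRF adjustment may still be needed. Section 14.8 requires IRB/IEC and regulatory approval of any amendment, so these edits are best bundled with the next one.

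If the sponsor prefers 8-weekly testing, the minimum is to delete the word monthly and state why the longer interval is acceptable.
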